14.2 Analysis Population

Subjects with less than 4 hours of valid oximetry and flow data in either the PSG or TatchSleep Pro recording (taking "movement" and "artifact" annotations into account following scoring – see protocol sections 8.4 and 8.5) will not be included in the analysis population [3]. All other participants who are enrolled, meet all the inclusion criteria and none of the exclusion criteria, and whose sleep studies have >4 hours of recorded and valid data from both systems will be included in the Analysis Population [3].

14.3 Safety Population

All participants who meet all of the inclusion criteria and none of the exclusion criteria and participated in the sleep study will be included in the Safety Population.

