9.1 Scoring Population

Studies of subjects whose TatchSleep Pro recording does not encompass the sleep period indicated by PSG will not be scored [3]. Studies from all other participants who are enrolled, meet all the inclusion criteria and none of the exclusion criteria, and whose PSG study has >4 hours of sleep duration will be scored [3].

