12.2 Severity

Adverse events will be classified by the investigator as mild, moderate, severe, life threatening, or fatal.

When the severity of the AE increases over time, the change in severity will be recorded in the source documents as a new AE and the original AE will stop when the new AE starts. The Principal Investigator or the delegated person must record all AEs that occur during the study from the time of TatchSleep Pro placement until study completion or Early Termination, regardless of their relationship to study device or procedure.

The Principal Investigator will evaluate the severity of AEs and determine their relationship to the study device or procedures. Any action or procedure followed by the patient or clinical staff to alleviate the AE will be documented regardless of who recommended such action or procedure. The clinical course of each event will be followed until resolution, stabilization, or clinically significant improvement that requires no further follow-ups in the opinion of the Investigator.

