12.4 Event Reporting

All AEs will be recorded on the CRF by the Investigator or designee regardless of their relationship to the study device. SAEs and ADEs should be reported to the Sponsor within 24 hours of knowledge of the event using the SAE/ADE Report Form provided by the Sponsor. UADEs must be reported by the clinical investigator to the sponsor and the reviewing IRB, no event later than 10 working days after the investigator first learns of the event. Sponsors must immediately conduct an evaluation of a UADE and must report the results of the evaluation to FDA, all reviewing IRBs, and participating investigators within 10 working days after the sponsor first receives notice of the effect.

13. Early Termination

Study patients may decide to withdraw from the research study without any penalty and for any reason. Study patients may be considered withdrawn if they state an intention to withdraw or fail to participate. Although patients are not required to provide a reason for withdrawal, they will be asked by research staff about their decision. The Investigator also reserves the right to remove a study participant from the study at any time for any reason (e.g. non-compliance with study requirements, safety reasons).

Study patients may also withdraw permission for the use and disclosure of any of their protected information for research but must do so in writing to the Principal Investigator.

14. Data Analysis

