14.1 General Considerations

Summary statistics for continuous variables will include the mean, standard deviation, median, and range. Categorical variables will be presented as counts and percentages. All confidence intervals provided will be calculated at the 95% confidence level, unless otherwise noted. All null hypotheses will be tested against two-sided alternatives at the 5% significance level, unless otherwise noted. Any other details not included in this protocol will be included in the Statistical Analysis Plan.

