14.7 Primary Safety Evaluation

The primary safety endpoints are the incidence of AEs and SAEs related to the device throughout the study period.

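### The Safety Population in 14.3 requires full eligibility, so a participant who wore the device and is later found ineligible falls outside every defined analysis set

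*Combined protocol and SAP*

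**What the plan says.** Section 14.3 defines the Safety Population in one sentence: "All participants who meet all of the inclusion criteria and none of the exclusion criteria and participated in the sleep study will be included". It sets two joint conditions, full eligibility and taking part in the sleep study.

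The other two defined sets carry the same eligibility condition. Section 9.1 (Scoring Population) reads "Studies from all other participants who are enrolled, meet all the inclusion criteria and none of the exclusion criteria", and 14.2 (Analysis Population) reads "All other participants who are enrolled, meet all the inclusion criteria and none of the exclusion criteria". Each then adds its own sleep-duration or data requirement.

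The collection rules are wider. Under 12.2 the investigator or delegate "must record all AEs that occur during the study from the time of TatchSleep Pro placement until study completion or Early Termination". Section 12.4 adds: "All AEs will be recorded on the CRF by the Investigator or designee regardless of their relationship to the study device". Neither mentions eligibility.

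Section 14.7 gives the endpoint without a population: "The primary safety endpoints are the incidence of AEs and SAEs related to the device throughout the study period". Section 14.1 supplies the format ("Categorical variables will be presented as counts and percentages") and a general deferral: "Any other details not included in this protocol will be included in the Statistical Analysis Plan".

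**The concern.** Whether a patch or oximeter harmed someone depends on whether it was worn, not on whether an eligibility check later stands up. The participation condition in 14.3 largely captures exposure already. The added eligibility condition can only remove people who were exposed, together with their events.

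No enrolled, all-treated or device-exposed set exists to catch them. Their adverse events would be on the CRF but would have no place in a population-based summary.

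At stake is the primary safety result. In a study of about 50 people, one omitted device-related event could change the report from one event to none.

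**Working it through.** No figure in the plan is in dispute, so the main check sets the rules side by side.

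| Rule | Eligibility required? | Other condition |
|---|---|---|
| AE recording (12.2, 12.4) | No | Event occurs after device placement |
| Scoring Population (9.1) | Yes | More than 4 hours of PSG sleep; device recording spans the sleep period |
| Analysis Population (14.2) | Yes | More than 4 hours of valid data from both systems |
| Safety Population (14.3) | Yes | Took part in the sleep study |

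A wearer later found ineligible meets the first row and fails the other three.

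**Can the case arise?** Sections 8.1 and 8.2 call for eligibility to be confirmed and for a Day 1 pregnancy test, so it should be uncommon. Two routes remain:

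- The opening of Section 6 describes participants from age 18, while 6.1 requires age 21. Someone aged 18 to 20 enrolled under the former would fall outside 14.3. The two passages must be reconciled.
- Some exclusions in 6.2, such as suspected sleep-related hypoventilation, could come to light during or after the recording.

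**Illustration.** Assumptions: 50 exposed participants (planned enrolment is about 50), exactly one device-related event, and one exposed participant later found ineligible. Only the 50 has a basis in the documents.

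- All exposed: 1/50 = 2.0% (exact 95% CI 0.05% to 10.6%).
- Under 14.3, event in the ineligible wearer: 0/49 = 0.0% (exact 95% CI 0% to 7.3%).
- Under 14.3, event in an eligible wearer: 1/49 = 2.04%.

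If events are unrelated to eligibility, the event falls in the ineligible wearer with probability 1/50 = 2%, given both assumed occurrences.

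**Prior safety information.** Section 11.3 reports no adverse events in 19 earlier full-night users. The exact two-sided 95% upper limit for 0/19 is 1 − 0.025^(1/19) = 17.6%. Applied to 50 people, that is 0.176 × 50 = 8.8 events. The earlier cohort therefore does not show that events will be rare; it is compatible with none and with several. If there is only one, its omission changes the conclusion a reader would draw.

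**The case against.** The strongest case against has four parts.

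- **Rarity.** Eligibility is checked before the night of the study, and most exclusions are history items that can be verified in advance. This stands: the gap should seldom be used, and the 1/50 to 0/49 change is an unlikely branch even under the assumed counts. It does not make the definition right.
- **The endpoint names no population.** Section 14.7 could be read as covering every recorded event. This also stands in part: the omission is an inference. But 14.3 defines a Safety Population that is given no other stated use, so the inference is the natural one.
- **A separate Statistical Analysis Plan may settle it.** The deferral in 14.1 reaches only matters the protocol leaves open. It could supply the denominator for 14.7, but it does not reach the Safety Population, which the protocol defines explicitly.
- **Nothing is hidden.** Events stay on the CRF, and the serious, device-effect and unanticipated-effect reports in 12.4 are unaffected. This is correct. The gap is in the summary endpoint, not in surveillance.

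Eligibility conditions are ordinary for effectiveness sets, so 9.1 and 14.2 are not faulted. They matter here only because they leave no fallback set.

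**Conclusion.** The concern holds, as a minor point. On the wording of 14.3 there is little doubt: the Safety Population is narrower than the group in whom adverse events are collected, and an exposed participant later found ineligible is in none of the three sets. That the event then drops out of the primary safety incidence rests on reading 14.7 as using the Safety Population.

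The size depends on counts the documents do not give. In the worst single-event case 2.0% is reported as 0.0%; otherwise the figure barely moves. The chance of such a case cannot be computed from the documents. Trial success is unaffected, because it rests on the three effectiveness null hypotheses in 14.5.

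**What to change.** 1. In 14.3, remove the eligibility condition and define the Safety Population as all participants on whom any TatchSleep Pro patch or the paired oximeter was placed. This matches the start of event recording in 12.2.
2. In 14.7, name the Safety Population as the denominator for device-related AEs and SAEs.
3. Report how many exposed participants were found ineligible.

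The first change corrects the rule; the other two make it explicit and visible. All should be made before analysis, so that the denominator is fixed before events are tabulated. The cost is wording in two sections and one reported count. The event data are already collected under 12.2 and 12.4, and neither the sample size nor any effectiveness test changes.

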14.4 Demographics

Demographic and baseline characteristics (age, sex, BMI, skin tone and presence of body hair) will be tabulated. The flowing table shows the measurement units/scale and approximate expected ranges for these characteristics:

Characteristic	Units or Scale	Expected Range
Sex	--	Male, Female
Age	Years	21-75
BMI	kg / m ²	23-40
Skin Tone	Fitzpatrick Scale	II - VI
Body Hair	--	No visible hair, moderate hair (≤ 10 follicles/cm ²), heavy hair (> 10 follicles/cm ²)

14.5 Primary Outcome Evaluation

The first co-primary performance objective is to demonstrate that the correlation between PSG and TATCH AHI is greater than the performance goal (PG) using a significance level of 0.025.

The hypotheses to be tested are:

$$H_0: \rho \leq PG \quad \text{versus} \quad H_a: \rho > PG$$

where ρ is the Pearson correlation between PSG and TatchSleep Pro AHI and PG is the performance goal. The performance goal is set to be 0.862, the lower 95% confidence limit for the correlation of RDI and AHI between PSG and Peripheral Arterial Tonometry (PAT) as calculated in a meta-analysis of 12 studies [5]. Fisher's transformation and one-sided Z-test will be used to test the hypotheses with a significance level of 0.025.

The second co-primary performance objective is to demonstrate that the 95% limits of agreement between PSG and TATCH AHI within the performance goals (PG_L and PG_U) using a significance level of 0.05.

The hypotheses to be tested are:

$$\begin{aligned} H_{01}: UL &\geq PG_U & \text{vs. } H_{a1}: UL < PG_U \\ H_{02}: LL &\leq PG_L & \text{vs. } H_{a2}: LL > PG_L \end{aligned}$$

where UL and LL are the upper and lower 95% limits of agreement between PSG and TATCH

AHI. The performance goals PG_U and PG_L are set to be the upper and lower limits, respectively, of the 95% confidence interval in a meta-analysis of 7 FDA approved devices (28.4 and -30.6). The full meta-analysis is detailed in Appendix 1. A Wald Z-test will be used to test the hypotheses with a significance level of 0.05. All three null hypotheses need to be rejected in order for the trial to be successful.

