14.6 Secondary Outcomes Evaluation

- A weighted Deming regression of TatchSleep Pro AHI on PSG AHI will be run. 95% confidence intervals for the slope and intercept will be obtained.
- The inter-rater reliability, measured as the intra-class correlation (ICC) of AHI readings and its 95% confidence interval will be calculated.
- Agreement between TatchSleep Pro and PSG apnea classification (mild, moderate, and severe, according to the American Academy of Sleep Medicine definition) will be calculated.
- Bland-Altman plots and estimation of the 95% limits of agreement between TatchSleep Pro and PSG AHI for each position (supine vs. non-supine).

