14.8 Sample Size

The correlation of PSG and TATCH AHI data on 19 subjects previously rated by a single rater was estimated to be 0.98. We calculated the probability of rejecting the null hypothesis when the true correlation is 0.98 using the Pearson's Correlation Tests Procedure of NCSS Power Analysis Statistical Software, Version 20 (PASS 20, [6]). A sample size of 46 subjects yields a power of 99.99%.

The ICC of PSG and TATCH AHI data on 19 subjects was 0.95, we use this as an estimate for the sample size calculation. A sample of 46 subjects yields a 95% margin of error for the ICC of 5%, assuming a true ICC value of 0.95, using the Confidence Intervals for Intraclass Correlation Procedure of NCSS Power Analysis Statistical Software, Version 20 (PASS 20, [6]).

The upper and lower limits of agreement of PSG and TATCH AHI data on 19 subjects previously rated by a single rater was estimated to be 10.6 and -3.2, with a standard deviation of 3.5. Because the standard deviation increases with increasing AHI, and the previous AHI range was 0 to 30 events/hour, we conservatively assumed a standard deviation of 7.0 events/hour, yielding a standard deviation for the LOA of $\sqrt{3}\sigma = 12.1$, as described in Bland-

Altman. We calculated the power to reject the null hypothesis using the One Sample T-Tests Procedure of NCSS Power Analysis Statistical Software, Version 20 (PASS 20, [6]). A sample size of 46 subjects yields an 99.9% probability of rejecting the null hypothesis for both the upper and lower LOAs.

A total sample size of 46 subjects yields sufficient power for the primary objective and allows for sufficient precision in estimating the inter-rater reliability, which is a secondary objective; approximately 50 subjects will be enrolled to allow for a 5-8% drop-out rate.

15. Study Administration

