Appendix 1 – Bland-Altman LOA Meta-Analysis

A meta-analysis was undertaken in support of developing a performance goal for the primary effectiveness endpoint of the Bland-Altman 95% limits of agreement (LOA). A total of 7 studies of 7 different FDA approved devices were chosen that used manual scoring of AHI in concurrent laboratory studies. A summary of the 7 devices used in the meta-analysis is provided in Table 1.

Table 1: Summary of Predicate HST Studies

Publication	Device	Reference	N	Lower 95% LOA	Upper 95% LOA	SD
Westbrook et al., 2005	ARES	Figure 6	187	-30.5	26.7	14.3
Massie et al., 2018	NightOwl	Figure 3	101	-38.9	39.6	20.0
Weiman et al., 2013	WatchPAT200	Figure 2	28	-13.6	19.5	8.4
Erman et al., 2007	ApneaLink	Figure 3	59	-21.3	18.0	10.0
Xu et al., 2017	Nox-T3 _{home}	Figure 1A	77	-26.6	17.4	11.0
Santos-Silva et al. 2009	Stardust	Figure 3D	80	-24.9	22.8	12.2
Nilius et al. 2017	Alice	Figure 3A	85	-13.5	10.3	5.9

A random effects model was utilized to generate an estimate of the average lower and upper LOA across the 7 studies. The random effects estimate was calculated using the Metafor [1] (Meta-Analysis Package for R) package. Restricted maximum likelihood was used to estimate the mean success rate and the variability among studies. The mean lower LOA and confidence intervals for each of the 7 studies, as well as the random effects (RE) summary results are presented in Figure 1; results for the upper LOA are presented in Figure 2. The random-effects model estimates a weighted least squares mean upper limit of 21.8 with a 95% confidence interval of 15.1 to 28.4; the random-effects model estimates a weighted least squares mean lower limit of -24.0 with a 95% confidence interval of -30.6 to -17.4. From this analysis, it is reasonable to use 28.4 for the upper limit performance goal and -30.6 as the lower limit performance goal for the LOA primary effectiveness endpoint analysis in our study.

Figure 1: Lower 95% LOAs for each study and 95% confidence intervals.

[figure not shown]
[figure not shown]

Figure 2: Upper 95% LOAs for each study and 95% confidence intervals.

References:

1. Viechtbauer, W. (2010). Conducting meta-analyses in R with the metaphor package. *Journal of Statistical Software*, 36(3), 1-48. <http://www.jstatsoft.org/v36/i03/>.

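### The Wald Z-test on each limit of agreement rejects at about 7.9%, not 5%, at n = 46, and its sidedness is not stated

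*Combined protocol and SAP*

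**What the plan says.** - Section 14.5 sets two directional hypotheses, upper limit below 28.4 and lower limit above -30.6, and then says: "A Wald Z-test will be used to test the hypotheses with a significance level of 0.05". No standard error is given. The words for a one-sided test appear only for the correlation.
- The same section makes this a gate for success: "All three null hypotheses need to be rejected in order for the trial to be successful".
- Section 14.1 sets the default: "All null hypotheses will be tested against two-sided alternatives at the 5% significance level, unless otherwise noted". It also defers detail: "Any other details not included in this protocol will be included in the Statistical Analysis Plan".
- Section 14.8 doubles the pilot SD of 3.5 to 7.0, "yielding a standard deviation for the LOA of" √3 × 7.0 = 12.1, and reports 99.9% power at n = 46 for both limits from a one-sample t-test procedure. Its reason for raising the SD is: "Because the standard deviation increases with increasing AHI, and the previous AHI range was 0 to 30 events/hour".
- Section 14.6 plans a weighted analysis elsewhere: "A weighted Deming regression of TatchSleep Pro AHI on PSG AHI will be run". Nothing comparable is planned for the test of the limits.

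**The concern.** A Wald test takes the estimate and its standard error as if the second were known. Here the estimate is mean ± 1.96s and the standard error is also a multiple of s. When s falls below the true SD by chance, the limit moves inside its goal and the standard error shrinks with it. Both errors favour rejection, and at about 46 subjects they do not average out. A device whose limit sits exactly on the goal would then pass a co-primary criterion more often than the protocol states.

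Two further points affect the level. The hypotheses are directional, so one-sided 0.05 per limit is the natural reading, but the 14.1 default points the other way and 14.5 does not settle it. The protocol also says that the SD rises with AHI, while the limits test assumes one SD for everyone.

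**Working it through.** **Inputs.** Goals 28.4 and -30.6 and level 0.05 (14.5). Variability of a limit √3·σ, planning SD 7.0, pilot limits 10.6 and -3.2, n = 46 with about 50 enrolled (14.8). Mean difference = (10.6 - 3.2)/2 = 3.7.

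**1. The plan's own figure.** The distances from the pilot limits to the goals are 28.4 - 10.6 = 17.8 and 30.6 - 3.2 = 27.4. With SD 7√3 = 12.1 and n = 46, one-sample t-test power exceeds 99.99% for both limits. Limits rebuilt with SD 7 are 3.7 ± 13.72, that is 17.42 and -10.02, with distances 10.98 and 20.58. Power again exceeds 99.99%, at one-sided 0.05 and at 0.025. This agrees with the stated 99.9%. That calculation treats the limit like a simple mean, so it cannot show the dependence between the limit and its standard error.

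**2. The Wald rule as a multiplier.** Reject for the upper limit if mean + 1.96s + z·s·√(3/n) < 28.4, that is mean + k·s < 28.4 with k = 1.96 + z·√(3/n). At n = 46, √(3/46) = 0.2554:
- z = 1.645: k = 2.380
- z = 1.960: k = 2.461

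**3. True size.** When the upper limit equals 28.4, √n·(28.4 - mean)/s follows a noncentral t distribution with n - 1 df and noncentrality 1.96√n. Size = P(T > k√n). The lower limit is the mirror image.

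| n | Nominal 5% | Nominal 2.5% |
|---|---|---|
| 46 | 7.9% | 4.9% |
| 50 | 7.7% | 4.8% |

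One million simulated trials at n = 46 gave 7.91% and 4.90%.

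**4. Other standard errors at n = 46** (nominal 5% / 2.5%).

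| SE divided by s | z critical value | t critical value |
|---|---|---|
| √(3/n) | 7.9 / 4.9% | 7.5 / 4.5% |
| √((1 + 1.96²/2)/n) | 8.2 / 5.1% | 7.8 / 4.7% |
| √(1/n + 1.96²/(2(n-1))) | 8.0 / 5.0% | 7.6 / 4.6% |

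**5. A bound with the right size.** Exact k = (noncentral-t quantile)/√n. At n = 46 this is 2.457 (0.05) or 2.566 (0.025); at n = 50 it is 2.432 or 2.536.

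**6. Effect on pass rates.** Upper limit, mean difference 3.7, n = 46, one-sided 0.05:

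| True SD | Wald | Exact |
|---|---|---|
| 7 | 99.99% | 99.98% |
| 8 | 99.2% | 98.3% |
| 9 | 90% | 84% |
| 10 | 64% | 54% |
| 11 | 34% | 26% |
| 12 | 14% | 10% |

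The upper limit reaches its goal at SD = (28.4 - 3.7)/1.96 = 12.6. Every row is below that, so the gaps show a looser standard of evidence, not false passes. In Appendix 1, five of the seven comparison devices have an SD of 10.0 or more (10.0, 11.0, 12.2, 14.3, 20.0), and two exceed 12.6.

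Taking tabulated limits from Appendix 1 as true (mean difference = midpoint, SD = half-width/1.96), both limits pass at n = 46, Wald against exact: 95.0% v 91.0% for (-21.3, 18.0), 43% v 34% for (-26.6, 17.4), 42% v 31% for (-24.9, 22.8), and 3.5% v 2.0% for (-30.5, 26.7).

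**The case against.** - **The standard error is inferred.** Section 14.5 gives none and 14.1 defers detail to the SAP. This stands as a condition on the 7.9%. But 14.5 already fixes a Wald Z-test, and the three usual standard errors all exceed the level. A score-type version, with the SD set at its boundary value (28.4 - mean)/1.96, has size 4.0% (1.6% at nominal 2.5%), but that is a different test.
- **On the two-sided reading, 4.9% is below 5%.** The nominal rate in the tested direction is then 2.5%, so the excess is about twofold.
- **All three nulls must be rejected.** Trial-level error therefore cannot exceed this gate's size and may be much smaller. With the upper limit on its goal (mean difference 3.7, SD 12.6), it depends on the spread of AHI. Under assumed normal AHI it runs from below 1% when the SD of AHI is 20 to about 7% when it is 30. The documents do not give that spread. The requirement caps the error but does not bring it to 5%.
- **Nothing changes at the planning SD.** True at 7.0. That SD is the doubled value from a 19-subject pilot with AHI 0 to 30, and the Appendix 1 devices show that larger values are plausible.
- **The exact bound also assumes constant SD.** This is the strongest point. In an assumed model with SD proportional to gamma-distributed AHI (mean 25, coefficient of variation 0.5 or 0.8), with the upper limit on its goal, the exact bound rejects 13% or 23% of the time and the Wald rule 17% or 27%. These figures depend on the model. They show that the exact bound is closer to its level but no cure for non-constant SD, so the assumption has to be stated and examined.

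**Conclusion.** The concern holds, and the test should be corrected. With the standard error from 14.8, normal differences and constant SD, each limits test has size 7.9% at n = 46 against 5% one-sided, or 4.9% against 2.5% if the two-sided default governs. On neither reading is the stated level the actual one, and the text does not say which reading applies. The practical effect is negligible at SD 7.0 and reaches about 10 percentage points in pass rate near SD 10. The further effect of an SD that rises with AHI cannot be derived from the documents.

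**What to change.** In 14.5 and the SAP:

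1. State that 0.05 is one-sided for each limit, or that 0.025 per side applies.
2. Replace the Wald rule with the exact noncentral-t bound: success if mean + k·s < 28.4 and mean - k·s > -30.6, with k = 2.457 (0.05) or 2.566 (0.025) at n = 46, recomputed for the number analysed (2.432 or 2.536 at n = 50).
3. State that the bound assumes normal, constant-SD differences. Add a supportive analysis in which the SD may vary with AHI, for example regression-based limits, labelled as sensitivity only.

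The cost is wording, a few lines of code and a slightly stricter criterion, with no added patients. At mean difference 3.7 and n = 46, the largest passing s falls from 24.7/2.380 = 10.38 to 24.7/2.457 = 10.05 (0.05), or from 24.7/2.461 = 10.04 to 24.7/2.566 = 9.63 (0.025). Upper-limit power with the exact bound is 99.98% or 99.90% at SD 7, and 98.3% or 95.7% at SD 8. Lower-limit power is above 99.99% at both SDs. If the true SD is 9 or more, the sponsor gives up the pass probability shown in the table in step 6.
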